12.2 Follow-up

Follow-up assessments will occur at specific intervals: within 2 months of the endovascular procedure (+ 1-month window), at 6 months (+/- 2-month window) and 12 months (+/- 2-month window) after randomisation. These assessments can be conducted in person (at a 2-month routine clinical appointment) or by telephone/video call/email communication. Early recruits will have additional follow-ups at 24 months (+/- 2-month window) and 36 months (+/- 2-month window) after revascularisation, if they reach those timepoints. The duration of follow-up will depend on the timing of entry into the trial, with follow-up ending either at 36, 24 or 12 months after revascularisation. The follow-up period will end 12 months (+/- 2-month window) after the last recruited participant has been randomised and initiates medication (at completion of their 12 follow-up assessments).

Participants will be sent two reminders by either the central research team or the research nurse via their chosen method of contact (text, email, post) to maximise follow-up.

Around 3 attempts will be made to contact the participant at each follow-up according to their preferred method of contact. If it is not possible to contact participants, a relative/carer may be contacted as an alternative. If all contact attempts are unsuccessful, a questionnaire booklet may be posted to the participants for them to complete and return. If a routine in-person outpatient visit is scheduled for clinical reasons within the follow-up visit windows, the follow-up questionnaires may be completed in-person, and/or clinical information collected at this visit may be used for follow-up assessments. Site staff will ensure, to the best of their knowledge, that participants are still alive before any contact attempts are made, by checking all local patient management systems available to them e.g. Spine data (England), Welsh Clinical Portal (Wales).

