15.1 Main analysis

The final analysis will be performed after the end of the trial follow-up period, which is 48 months after the start of recruitment. Baseline demographic and clinical characteristics will be summarised descriptively by arm.

The primary analysis will be an intention to treat (ITT), including all randomised participants with non-zero follow-up time.

For the composite primary outcome (time from randomisation to the first occurrence of any element of the composite), a two-level Cox proportional hazards regression model will be fitted to estimate hazard ratios, including fixed effects for allocation and random effects to model heterogeneity between sites. Participants are censored at the end of the planned follow-up period (36 months), at

the end of the trial follow-up period, or (in case of dropout) at the time of their last follow-up, whichever occurs first. Regression analysis results will be presented as point estimates with confidence intervals and p-values from a log-rank test, and Kaplan-Meier curves of cumulative event rates at 36 months (31,32) will be generated to compare arms over time.

Primary estimand

Primary outcome question: In patients following endovascular intervention for CLTI, what is the event-free survival time of the three commonly used antithrombotic regimens (clopidogrel; aspirin plus clopidogrel; aspirin plus low-dose rivaroxaban), for those with a non-zero follow-up time?

The primary estimand is described by the following attributes:

- Population: Adults who are first time in CLARITY trial undergoing percutaneous or hybrid endovascular intervention for CLTI of the lower limbs, with atherosclerosis as the cause of CLTI, and with non-zero follow-up time.
- **Endpoint**: The clinical effectiveness endpoint is a composite event-free survival time examined over the trial duration. These events included acute limb ischaemia, major lower limb amputation, myocardial infarction, ischaemic stroke, and all-cause mortality. Participants are censored at the end of the planned follow-up period (36 months), at the end of the trial follow-up period, or (in case of dropout) at the time of their last follow-up, whichever occurs first.
- **Treatment condition**: Clopidogrel, aspirin plus clopidogrel, and aspirin plus low-dose rivaroxaban, regardless of discontinuation or initiation of the antithrombotic regimens.

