At a local level, we will interact with and promote research findings through wider NHS Trusts and the NIHR Clinical Research Networks. Nationally, we will engage with NICE, the Vascular Society of Great Britain and Ireland, the British Society of Interventional Radiology, the British Society for Endovascular Therapy, the Vascular Anaesthesia Society of Great Britain and Ireland, and the Vascular and Endovascular Research Network, as well as relevant charities such as the Douglas Bader Foundation. We anticipate the results directly impacting clinical antithrombotic guidelines, which to date do not

include recommendations regarding optimal antiplatelet/anticoagulant usage post-endovascular intervention.

26 Milestones

The CLARITY trial is a five-year trial with the following project timetable:

- Month 1-8: Trial and site set-up, contracts, regulatory approvals.
- Month 9-17: Internal pilot (assessed by progression criteria) and recruitment. Assess the acceptability of intervention and trial processes.
- Month 18-54: Continuation of RCT recruitment, follow-up and data collection, and interim analysis (when 60% of primary outcome events have been observed).
- Month 55-60: Data cleaning, statistical analysis, preparing HTA report, draft papers, and dissemination activities.

27 References

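### Section 12.2 ends each participant's follow-up at the 12, 24 or 36-month visit, but section 15.1 counts them at risk to 36 months or recruitment month 48, so about 13% of person-time has no scheduled event ascertainment.

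*Protocol*

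**What the plan says.** **Participant level.** Section 12.2 makes the length of follow-up depend on entry time, "with follow-up ending either at 36, 24 or 12 months after revascularisation". Section 12.1 and Table 2 schedule primary and bleeding outcome assessment at 2, 6, 12, 24 and 36 months only. Section 13.5.1 ends SAE reporting no later than the final 12, 24 or 36-month visit.

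**Trial level.** Section 12.2 also says: "The follow-up period will end 12 months (+/- 2-month window) after the last recruited participant has been randomised and initiates medication". Section 15.1 places the final analysis after "the end of the trial follow-up period, which is 48 months after the start of recruitment". With 36 months of recruitment these two agree, since 36 + 12 = 48.

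**Censoring of the primary outcome.** Section 15.1, repeated in the primary estimand, says: "Participants are censored at the end of the planned follow-up period (36 months), at the end of the trial follow-up period". The last follow-up is the censoring date only for dropouts: "at the end of the trial follow-up period, or (in case of dropout) at the time of their last follow-up".

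**Timetable.** Section 26 starts the pilot and recruitment in project month 9. It then gives "Month 18-54: Continuation of RCT recruitment, follow-up and data collection" and "Month 55-60: Data cleaning, statistical analysis".

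**The concern.** The visit schedule and the censoring rule do not describe the same follow-up. A participant who completes every visit is not a dropout. Section 15.1 therefore carries that participant forward as event-free to month 48 of recruitment (or 36 months), although sites were told that follow-up ended at the last annual visit.

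Take someone randomised 18 months into recruitment. Section 15.1 counts 48 − 18 = 30 months at risk. The last visit is at 24 months, and the window for the 36-month visit does not open until month 34. Several months of event-free time are then credited without a planned look.

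If events in that time are missed, event rates are understated. Allocation is known to patients and clinicians (section 14.2), so reporting without a scheduled visit could differ by arm. If sites instead follow the participant-level clause strictly, events in that time are not collected, although section 15.1 assumes that they are. The analysis plan cannot fully repair this later, because it cannot create data that sites were told to stop collecting.

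**Working it through.** **Inputs (section 14.3).** Control 12-month event-free rate 65.0%; hazard ratio 0.65; dropout 8% per year; 413 per arm; accrual 25%, 35% and 40% in years 1, 2 and 3; two-sided alpha 2.5% per comparison. Assumption added here: accrual is uniform within each year.

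**Hazards per year.** Control λ = −ln 0.65 = 0.431. Combination arms λ = 0.65 × 0.431 = 0.280. Dropout δ = −ln 0.92 = 0.083.

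**Formulas.** For planned follow-up t, expected person-years are PY(t) = [1 − exp(−(λ+δ)t)]/(λ+δ), and expected events are λ·PY(t). Both are averaged over entry time and multiplied by 413.

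**The plan's own figure.** The protocol states 157 + 115 + 115 = 387 events. Stopping all follow-up at recruitment month 36 gives 157.0 + 114.3 + 114.3 = 386. Of the cut-offs tried, only this one reproduces the stated count, and it allows no follow-up after recruitment closes. So section 14.3 does not settle which end of follow-up is meant.

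**Candidate ends of follow-up**

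| Rule | Control | Each combination arm | Total events | Person-years |
|---|---|---|---|---|
| Month 48, 36-month cap (15.1) | 229.0 | 172.1 | 573 | 1,761 |
| Last 12/24/36-month visit (12.2) | 201.4 | 149.1 | 500 | 1,533 |
| Recruitment month 46 (26) | 220.0 | 164.5 | 549 | 1,686 |

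**Gap between 15.1 and 12.2**
- Person-time: 1,761 − 1,533 = 228 person-years; 228/1,761 = 13%.
- Events: 573 − 500 = 73.
- Who is affected: year-1 recruits (25%) reach 36 months, so no gap. Year-2 recruits (35%) are at risk for 24 to 36 months with a last visit at 24. Year-3 recruits (40%) are at risk for 12 to 24 months with a last visit at 12. So 35% + 40% = 75% have a gap of up to 12 months, with a mean of 6.

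**Allowing for the ±2-month windows**
- If a visit counts once its early edge is reached: 521 events, a gap of 573 − 521 = 52 (9%).
- If the 12- and 24-month visits are also held at their late edge, as an upper bound: 541 events, a gap of 573 − 541 = 32 (6%). Half of participants still have a gap.

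**Power per comparison (Schoenfeld).** Φ(√(D/4)·|ln 0.65| − 2.241)
- Month 48: D = 229.0 + 172.1 = 401.1, giving Φ(4.31 − 2.24) = 0.98.
- Last visit: D = 201.4 + 149.1 = 350.5, giving Φ(4.03 − 2.24) = 0.96.

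**Milestones.** Project months 9 to 54 inclusive are 54 − 9 + 1 = 46 months. Forty-eight months would end at project month 8 + 48 = 56, inside the cleaning period. Recruits in the last two months: 1,239 × 0.40/12 × 2 = 83.

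**The case against.** **Ascertainment does not stop at the last visit.** Section 12.1.1 provides a contact card and a GP letter, section 13 requires primary events on a CRF within 24 hours of knowledge, and section 16.1 has sites record events as they arise. Medical notes are a source for the primary outcome, and section 12.1 allows assessment from patient records. This stands. A reader might infer that events in the gap are lost, or that event rates will be biased. The documents do not support that; they show only that no look is scheduled in that time.

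**The windows shrink the gap.** This also stands. Someone recruited in month 13 has about 35 months at risk and can have an in-window 36-month visit. The gap narrows to 6–9% of expected events but does not close.

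**A larger share might be inferred.** Mean planned follow-up is 26.7 against 22.2 months, a difference of 17%. That ignores events and dropout. On person-time at risk the share is 13%.

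**Stopping at the last completed scheduled visit is a legitimate rule.** It is, and its cost in power is small. But section 15.1 does not adopt it for participants who complete follow-up.

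**The milestones create no unobserved time.** Correct. An earlier data stop shortens follow-up, and the two months equal the lower edge of the 12-month window. It is a separate timetable error.

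**Conclusion.** The conflict is real and sits in operative text, but it is narrow: one participant-level clause in section 12.2, together with the visit schedule and the SAE reporting period in 13.5.1, against the censoring rule in section 15.1. It would be wrong to infer that every statement of the end of follow-up disagrees, because the trial-level sentence in 12.2 matches month 48.

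Read as written, about 75% of participants are credited with event-free time after their last scheduled assessment. That is about 13% of person-time and 73 of 573 expected events, or 32–52 events if the windows are fully used. These figures rest on the section 14.3 assumptions and uniform accrual within years. The harm is a risk of under-ascertainment, possibly differing by arm. The size of any such bias cannot be derived from the protocol. A shortage of events should not be inferred: every candidate rule exceeds the stated 387, and power stays at about 0.96 or above.

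Separately, section 26 falls two months short of month 48. About 83 late recruits would have nominally less than the 12-month minimum stated in sections 12 and 14.3, although an in-window 12-month visit remains possible. The protocol should be corrected, and this is easiest before sites begin closing participants at their last visit.

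**What to change.** State one closing rule in sections 12.2, 15.1 and 26: primary and bleeding events are followed to 36 months or to a common close-out at recruitment month 48, whichever is first. Add a records-only event and vital-status check for every participant at close-out, using the medical notes and the patient management systems that section 12.2 already names. Reconcile the event-reporting period in section 13.5.1 with that rule. Move the end of data collection in section 26 to project month 56, with cleaning and analysis in months 57–60.

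The cost is protocol wording, one record check per participant, and two months less for cleaning and analysis (or a short extension).

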12.2.1 Month 2 – Clinical follow-up

Within two months of the revascularisation, data from the routine clinical follow-up appointment, attended by the patients and conducted by their clinicians, will be collected by research staff. Current medications, all primary composite and bleeding outcomes, and all secondary and tertiary outcomes other than health economic data will be assessed, including:

Primary composite and bleeding outcomes

- 1. A composite event-free survival time of:
 - i. acute limb ischaemia
 - ii. major lower limb amputation
 - iii. myocardial infarction
 - iv. ischaemic stroke
 - v. all-cause mortality
- 2. Major bleeding

Secondary outcomes

- 1. Major adverse limb events (MALE) defined as amputation or any major reintervention;
- 2. Major adverse cardiovascular events (MACE) defined as recurrent CLTI, amputation affecting the contralateral limb, acute coronary syndrome or stroke;
- 3. BARC and TIMI major bleeding;
- 4. Minor bleeding;
- 5. Primary and secondary patency of artery;
- 6. Reintervention rates;
- 7. Healing of tissue loss;
- 8. Participant-reported health-related QoL (VascuQoL-6 and EQ-5D-5L);

- Current medications (including changes to trial drugs and reasons)
- Tertiary outcomes
- MALE using other major definitions
- 2. MACE using other major definitions
- 3. Complications from trial medications

12.2.2 Month 6 and Month 12 (and Months 24 and 36 if applicable) – follow-up

All outcomes measured at 2 months will be assessed at the 6- and 12-months follow-up time points for all participants, and also at 24 and 36 months for those recruited earlier.

A healthcare resource use CRF/Questionnaire (adapted CSRI) will additionally collect:

- Hospital admissions, emergency department attendance and outpatient attendance via medical notes.
- Community-based resource use via patient-reported questionnaire supported by a patient diary as an *aide mémoire*.

12.2.3 Longer-term follow-up

Participants will be asked to consent to data-linked longer-term follow-up. Should our results indicate longer-term follow-up is desirable (for example, to further explore the impact of the trial medications on the primary effectiveness or safety outcome events), we will apply for further funding.

12.3 Qualitative Process Evaluation

12.3.1 Objectives

The objectives of the qualitative study are:

- To conduct a process evaluation of the CLARITY trial: Evaluate the delivery of the CLARITY trial and trial interventions through exploring trial conduct, trial acceptability (including barriers and facilitators to recruitment and retention), intervention adherence and contextual factors affecting trial delivery.
- To explore how the trial interventions work in the real healthcare setting: Explore feasibility, participant responses, acceptability to health professionals and patients, implementation, practicality and contextual factors that shape how the interventions work.

12.3.2 Semi-structured interviews

Semi-structured interviews will be conducted with a sample of CLARITY trial participants, patients who are eligible for the trial but decline to participate and health professionals involved in trial delivery. This method has been chosen to encourage participants to initiate and elaborate on topics most important to them which may not have been pre-empted if using survey-type closed questions.

Interview topic guides will be developed by the qualitative researchers in consultation with the CLARITY trial team and PPI representatives. Interview questions will then be developed iteratively in response to evolving study findings. The first five interviews with patients and the first five interviews with health professionals will be used as a pilot and interview questions reviewed after the pilot interviews have been carried out. Data from these interviews will be included in the analysis. Field notes will be made where applicable.

Interviews will explore contextual factors that shape how the trial interventions work in practice, patient responses to the interventions (e.g. acceptability and adherence), trial conduct, barriers and facilitators to trial recruitment and retention (including reasons for declining trial participation, where applicable), and patients' understanding of the trial, consent and randomisation process. Interviews will also explore patients' and clinicians' views on the balance of bleeding risk vs. gain (ischaemic events prevented), to better understand views on the 'net benefit' of antithrombotic therapy.

Through the qualitative interviews, the researcher will gain an impression of participants' understanding of the trial, consent and randomisation process. Any actionable points from the interviews will be reported to the TMG promptly so that if understanding remains poor, the TMG can propose solutions, review these with the PPI representatives, and present them to the TSC rapidly.

Depending on location and participant preference, interviews may be conducted via telephone/videocall or face-to-face. Face-to-face interviews with health professionals will be conducted at the participant's workplace. Face-to-face interviews with patients may take place in a private room in the hospital or at the patient's home. Lone working procedures will be followed where applicable. Patients will be invited to include a relative or friend in the interview if they wish. Interviews may bring back memories of a difficult and distressing time for participants – if participants become upset the interview can be stopped at any time, and the qualitative researcher will direct the participant to more support if required.

A password-protected Cardiff University laptop will be used to conduct telephone/videocall interviews. Interviews will be recorded using a password-protected digital voice recorder or a password-protected Cardiff University laptop.

12.3.3 Recruitment and sampling

We will aim to carry out patient interviews at around 1-3 months following trial enrolment (or following their invitation to participate in the trial), aiming to ensure patients have had sufficient time to recover from their endovascular intervention procedure and to be able to reflect on their experiences of the trial intervention if applicable. We will aim to carry out health professional interviews from the middle of the site's involvement in the trial so that health professionals can comment on any initial issues while having sufficient experience running the trial.

Potential interview participants (patients and clinicians) will be given a PIS about the qualitative interview study by the Research Nurse or local site PI. Once they have had time to consider the study information, potential interview participants will be asked by the local site PI or Research Nurse to complete a consent to contact form and consent form, which will be securely electronically transferred from the site to the research team. The qualitative researcher may then contact them directly to arrange a suitable time for an interview. If a completed consent form is not received, consent will be taken over the telephone/ videocall and recorded before the start of the interview.

Patient participants will be reimbursed for their time with a £20 gift voucher for taking part in the qualitative interviews. No other financial incentives will be provided for participants enrolled on the study.

Interview participants will be sampled purposively to maximise diversity. The sampling strategy for patients will be developed to include participants from each of the three treatment allocation arms (if applicable) and different trial sites, aiming for a range in terms of age, gender and ethnicity. The sample strategy for health professionals will be developed to include representation from around 4-6

different trial sites and variations in HCP roles (e.g. Research Nurse, Vascular Surgeon, Interventional Radiologist). We anticipate that interviews with around 10-20 health professionals and 20-30 patients (including up to 10 patients who have declined to participate in the trial) will be sufficient to encompass a breadth of views. The qualitative researchers will make pragmatic decisions in consultation with the trial team regarding when enough is known about certain themes (i.e. data saturation has occurred) and no further sampling is necessary.

13 Pharmacovigilance

The PI at each site is responsible for ensuring that all site staff involved in this trial are familiar with the content of this section.

All serious adverse events (SAEs) must be reported immediately (and within 24 hours of knowledge of the event) by the PI at the participating site to the CTR PV and Safety Specialist unless the SAE is specified as not requiring immediate reporting (see section 13.2). This includes SAEs related to IMPs.

The trial population comprises mainly elderly, unwell participants. Acute limb ischaemia, major amputation, myocardial infarction, ischaemic stroke, major bleeding and death are common. As these are composite primary outcomes of the trial, they will be recorded on the Primary Composite and Bleeding Outcomes CRF as part of data collection within 24 hours of knowledge of the event, and therefore not subject to expedited reporting on an SAE form. See the Adverse event reporting procedures flow diagram (Figure 2 on page 44).

13.1 Definitions

Table 3. Definitions of Adverse and Serious Adverse Events and Reactions

Term	Definition
Adverse Event (AE)	Any untoward medical occurrence in a participant or clinical trial participant administered a medicinal product and which is not necessarily caused by or related to that product
Adverse Reaction (AR)	Any untoward and unintended response in a clinical trial participant to an investigational medicinal product which is related to any dose administered to that participant
Serious Adverse Event (SAE)	Any adverse event that - Results in death Is life-threatening* Required hospitalisation or prolongation of existing hospitalisation** Results in persistent or significant disability or incapacity Consists of a congenital anomaly or birth defect Other medically important condition***
Serious Adverse Reactions (SARs)	Any SAE occurring in a clinical trial participant for which there is a reasonable possibility that it is related to the IMP at any dose administered.
Suspected Unexpected Serious Adverse Reactions (SUSARs)	A SAR, the nature and severity of which is not consistent with the Reference Safety Information (RSI) for the IMP.

- *Note: The term 'life-threatening' in the definition of serious refers to an event in which the trial participant was at risk of death at the time of the event or it is suspected that used or continued use of the product would result in the subjects death; it does not refer to an event which hypothetically might have caused death if it were more severe.
- ** Note: Hospitalisation is defined as an inpatient admission, regardless of the length of stay, even if the hospitalisation is a precautionary measure for continued observation. Pre-planned hospitalisation e.g. for pre-existing conditions which have not worsened, or elective procedures, does not constitute an SAE.
- *** Note: other events that may not result in death, are not life-threatening, or do not require hospitalisation, may be considered as an SAE when, based upon appropriate medical judgement, the event may jeopardise the participant and may require medical or surgical intervention to prevent one of the outcomes listed above.

